9.2.2 The query process

The monitor shall review the eCRFs and evaluate them for completeness and consistency. Each eCRF shall be compared with the respective source documents to ensure that there are no discrepancies between critical data. All entries, corrections, and alterations shall be made by the PI or his/her authorized designee. The monitor cannot enter data in the eCRFs. Once study data have been submitted to the central server via the eCRF, corrections to the data fields will be audit trailed, meaning that the reason for change, the name of the person who made the change, together with time and date will be logged. Roles and rights of the site personnel responsible for entering study data into the eCRF shall be determined in advance. If discrepant data is detected during review of the data, either by the Sponsor or by its representatives, the responsible data manager or monitor shall raise a query in the electronic data capture application. The query shall state the question or data to be changed and shall be resolved in the system by the PI or his/her authorized designee. The appropriate study site personnel shall answer the queries in the eCRF. This will be audit trailed by the electronic data capture application meaning that the name of study site personnel, time, and date is logged.

9.2.3 User identification

Electronic CRF records will be automatically appended with the identification of the creator, by means of their unique UserID. Specified records shall be electronically signed by the Investigator to document his/her review of the data and acknowledgement that the data are accurate. This will be facilitated by means of the Investigator's unique UserID and password;

date and time stamps will be added automatically at time of electronic signature. If an entry in an eCRF requires change, the correction shall be made in accordance with the relevant software procedures.

9.2.4 Audit trail

All changes will be fully recorded in a protected audit trail and a reason for the change shall be stated. Once all data have been entered, verified, and validated, the database will be locked.

9.3 Source documents

The eCRF is essentially considered a data entry form and does not constitute the original (or source) medical records unless otherwise specified. Source documents are all documents used by the Investigator or hospital that relate to the subject's medical history, that verifies the existence of the subject, the inclusion and exclusion criteria, and all records covering the subject's participation in the study. They include laboratory notes, memoranda, material dispensing records, subject files, etc.

The PI is responsible for maintaining adequate and accurate source documents. Source data should be attributable, legible, contemporaneous, original, accurate, and complete. Changes to source data should be traceable, should not obscure the original entry and should be explained if necessary.

These shall be made available for inspection by the monitor at each monitoring visit. The Investigator must submit a completed eCRF for each subject for whom signed informed consent has been collected. All supportive documentation submitted with the eCRF, such as laboratory or hospital records, shall be clearly identified with the clinical trial number (CTN) and subject number. Any personal information, including name, shall be removed or rendered illegible to preserve individual confidentiality.

9.4 Record keeping and access to source data

The PI/Institution shall permit study-related monitoring, audits, IEC review, and RA inspections and shall provide direct access to the source data/medical record including the identity of all participating subjects (sufficient information to link records, i.e. eCRF, medical records, original signed informed consent forms and detailed records of study product accountability). The records shall be retained by the PI as required by local legislation and international guidelines. Any transfer of responsibility for storage of the records shall be documented and the Sponsor shall be informed in writing.

The Sponsor shall verify that each subject has consented in writing to direct access to the original medical record/source data (by the use of written subject information and signed informed consent). The data recorded in the eCRFs will be checked for consistency with the source documents/medical record by the monitor during monitoring (source data verification; SDV). In order to be able to perform SDV, information about each subject's participation in the study has to be detailed in the medical record or other relevant source.

9.5 Document and data retention

All records pertaining to the conduct of the study, including signed eCRFs, informed consent forms, study product accountability records, source documents, and other study documentation must be retained for 25 years after study completion or longer if required by national legislation. Sponsor will inform the site(s) as to when these documents no longer

needs to be retained. Measures shall be taken to prevent accidental or premature destruction of these documents (e.g. protection against damage and unauthorized access, preferably by storage in a fireproof cabinet).

It is the PI's responsibility to inform the Sponsor in writing if the Investigator file is moved or if the responsibility for the documents is transferred to someone else.

10. Statistical Methods

10.1 General

A large rectangular area of the page is completely blacked out, indicating that the content has been redacted.

10.3 Demographics, baseline assessments, and subject characteristics

Demographic endpoints, baseline assessments, and subject characteristics will be presented based on the FAS, using descriptive statistics.

10.4 Efficacy analysis

A large rectangular area of the page is completely blacked out, indicating that the content has been redacted.

10.5 Safety analysis

AEs will be coded according to MedDRA and summarized by system organ class (SOC), preferred term (PT).

10.6 Handling of missing data

Study data will be presented based on observed cases, i.e. no imputation of missing values will be performed.

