3.1 Objectives and endpoints

3.1.1 Primary objective and endpoint

Aesthetic improvement (overall appearance) with Restylane Kysse compared to pre-treatment, assessed by the subject 8 weeks after last treatment, using the Global Aesthetic Improvement Scale (GAIS). The response rate is defined as a subject with a rating of at least “Improved”.

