4.1 General outline

This is an open-label, phase IV, post-marketing study to evaluate aesthetic improvement and partner/subject satisfaction after treatment with Restylane Kysse, alone and in combination with Restylane Defyne and Restylane Refyne.

Approximately 50 to 60 subjects at 4 sites in Canada will be treated. Twenty subjects will be treated with Restylane Kysse in the lips only (Group A) and 30 to 40 subjects will be treated with Restylane Kysse in the lips and Restylane Defyne and/or Restylane Refyne in the facial wrinkles and folds (Group B). All injections will be per the IFUs. Optional touch-up treatment at Week 4 is allowed for all products injected at initial treatment.

The treating investigator will determine if a subject is placed in Group A or B based on the optimal outcome for the subject.

[figure not shown]
Adult women and men who have a steady relationship with a partner for 6 months and intend to undergo lip augmentation will be asked to participate in the study. Eligible subjects will be injected by the Treating Investigator at Day 1. If optimal correction of the lips or surrounding facial wrinkles and folds (if treated) is not achieved at the first treatment or if the aesthetic appearance could be further improved, a touch-up will be offered after 4 weeks; this decision should be agreed upon by the Treating Investigator and the subject. Touch-up treatment will not be performed if the subject has a disease or condition described in the exclusion criteria, or an ongoing treatment-related AE that in the opinion of the Treating Investigator would be worsened by a touch-up treatment.

The subjects will be treated to achieve optimal correction. Optimal correction is defined as the best possible aesthetic outcome as agreed to by the Treating Investigator and the subject.

The maximum volume recommended for both initial and touch-up treatments combined is 2.5 mL for Restylane Kysse, 6.0 mL for Restylane Defyne and 4.0 mL for Restylane Refyne.

Subjects will be contacted by telephone 72 hours after initial treatment and optional touch-up treatment (as applicable) and will have in-clinic follow up visits at 4 weeks and 8 weeks after the last treatment.

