5.5 Withdrawal of subjects

An Investigator may decide to discontinue a subject from the clinical study for safety reasons.

Although the importance of completing the entire clinical study should be explained to the subject by the clinical study personnel, any subject is free to discontinue participation in this clinical study at any time and for whatever reason, specified or unspecified, and without any prejudice. No constraints are to be imposed on the subject, and when appropriate, a subject may be treated with other conventional therapy when clinically indicated.

When a subject does not complete the clinical study, he/she will be fully assessed, if such assessment is possible. The procedures designated for the Early Termination (ET) visit should be completed for all subjects discontinuing the clinical study and the appropriate eCRF should be completed.

[figure not shown]
All discontinuations and the reason for discontinuation are to be documented by the Investigator.

For discontinuation due to an AE, the Adverse Event form is to be completed. The Investigator should also ensure that the subject receives suitable therapy for the AE.

Pregnancies occurring during the screening period are considered as screening failures; they should be recorded as such in the eCRF and no pregnancy form is to be completed.

In case of a pregnancy occurring after the baseline visit, the procedures described in Section 8.2.8 should be followed. The subject may remain in the study, but no invasive procedure should be conducted.

The Sponsor may also decide to prematurely terminate or suspend a subject's participation in the clinical study.

If an AE which, according to the Investigator's assessment, is related to the use of any of the study products and is still ongoing at the time of the withdrawal, the Investigator shall follow-up the subject until the AE resolves, is assessed by the Investigator to be "chronic" or "stable" or for at least 3 months.

6. Study Product

The term "study product" refers to Restylane Kysse, Restylane Defyne and Restylane Refyne.

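### The primary GAIS response rate is on observed cases only, and the visible text adds no figure that keeps all treated subjects in the denominator

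*Protocol*

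**What the plan says.** The primary endpoint (Protocol 3.1.1) is overall aesthetic improvement compared with pre-treatment, rated by the subject on the GAIS 8 weeks after last treatment. A responder is defined in these words: "The response rate is defined as a subject with a rating of at least “Improved". The definition does not say how a subject with no rating is classified.

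Protocol 10.6 governs missing data: "Study data will be presented based on observed cases, i.e. no imputation of missing values will be performed". It is worded for all study data and names no exception.

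The design (Protocol 4.1) is open-label. "Approximately 50 to 60 subjects at 4 sites in Canada will be treated", split by investigator choice into Group A (20, lips only) and Group B (30 to 40, lips plus surrounding folds). Section 6.2 states that there is no reference product.

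Two other passages bear on incomplete subjects. Section 5.5 says: "The procedures designated for the Early Termination (ET) visit should be completed for all subjects discontinuing the clinical study". Section 10.8 has withdrawn subjects listed one by one with date, reason and last visit.

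Sections 10.1 and 10.4 (which holds 10.4.1, the primary analysis) are redacted, the title of 10.2 is redacted, and the schedule of events and Section 7 cannot be read. The SAP supplied describes a different trial: randomized 2:1, about 280 subjects, non-inferiority, 48 weeks.

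**The concern.** Under 10.6 as written, a treated subject with no countable rating is in neither the numerator nor the denominator of the response rate. Counting that subject as a non-responder would itself be an imputation, which 10.6 rules out.

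In a controlled trial, similar loss in both arms would partly cancel in the comparison. Here the result is a single proportion, rated by subjects who know what they received. Groups A and B are formed by the investigator's judgement, so neither is a control for the other. A subject unhappy with the outcome is a plausible non-returner, although nothing in the documents shows that this happens. If it does, the main efficacy figure of a study that Section 2.3 says is done for marketing purposes is too high, and the observed-case figure alone does not show by how much.

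**Working it through.** The visible text states no response rate, loss rate or sample-size derivation, so there is no plan figure to reproduce. The group sizes are consistent: 20 + 30 = 50 and 20 + 40 = 60.

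**Inputs.** Number treated N = 50 to 60, and Group A = 20 (Protocol 4.1). Everything else is assumed: the number missing m, the true response rate p, and the dropout rates dR (responders) and dN (non-responders).

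**Step 1: bias of the observed-case rate.**

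Expected observed rate = p(1 − dR) / [p(1 − dR) + (1 − p)(1 − dN)]

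| p | dR | dN | Observed rate | Bias (points) |
|---|---|---|---|---|
| 80% | 10% | 10% | 0.72/0.90 = 80.0% | 0 |
| 80% | 5% | 10% | 0.76/0.94 = 80.9% | +0.9 |
| 80% | 5% | 30% | 0.76/0.90 = 84.4% | +4.4 |
| 80% | 5% | 50% | 0.76/0.86 = 88.4% | +8.4 |
| 90% | 5% | 30% | 0.855/0.925 = 92.4% | +2.4 |
| 90% | 5% | 50% | 0.855/0.905 = 94.5% | +4.5 |

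The direction depends only on whether dN exceeds dR. The +2 to +8 range needs non-responders to leave six to ten times as often as responders; a twofold difference (5% and 10%) moves the rate by less than one point.

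**Step 2: worst-case gap.** With x responders among the N − m subjects rated:

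- Observed-case rate = x/(N − m)
- Rate with missing as non-response = x/N
- Gap = observed rate × m/N

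| N | m | Observed cases | Missing as non-response | Gap (points) |
|---|---|---|---|---|
| 60 | 3 (5%) | 54/57 = 94.7% | 54/60 = 90.0% | 4.7 |
| 50 | 5 (10%) | 43/45 = 95.6% | 43/50 = 86.0% | 9.6 |
| 55 | 6 (10.9%) | 47/49 = 95.9% | 47/55 = 85.5% | 10.5 |
| 60 | 9 (15%) | 48/51 = 94.1% | 48/60 = 80.0% | 14.1 |
| 20 (Group A) | 2 (10%) | 16/18 = 88.9% | 16/20 = 80.0% | 8.9 |

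Gaps are taken from unrounded rates. For N = 55 with 6 missing, the exact (Clopper-Pearson) 95% interval is 86.0% to 99.5% on observed cases and 73.3% to 93.5% with missing as non-response. If all six missing subjects were responders, the rate would be 53/55 = 96.4%. The observed-case figure of 95.9% thus lies near the top of the range that the missing ratings allow (85.5% to 96.4%).

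**Step 3: bias of the alternative.** Expected rate with missing as non-response = p(1 − dR). At dR = 5% this is 76.0% for p = 80% (−4.0 points) and 85.5% for p = 90% (−4.5). At dR = 10% it is 72.0% (−8.0) and 81.0% (−9.0). It is a lower bound and understates the true rate whenever any responder is lost.

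**The case against.** A reader might infer that the plan contains no check on the primary figure. The documents do not support that. The primary analysis section is redacted, the definition of the full analysis set is not visible, and either could fix the denominator or add a sensitivity analysis. What can be said is that 10.6, the section devoted to missing data, is visible and makes no exception.

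A reader might also infer that every subject who leaves early is lost from the rate. Section 5.5 asks for Early Termination procedures in all who discontinue. Whether these include the GAIS, and whether such a rating would count, cannot be seen. Some ratings may be recovered.

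The mechanism is not documented either. The touch-up offered at Week 4 gives a dissatisfied subject a reason to come back, and satisfied subjects may skip the last visit, which would bias the rate downward. The rule therefore does not necessarily flatter the result.

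The listing in 10.8, with the number treated, lets a reader work out a worst case for withdrawn subjects. It does not obviously cover subjects who stay in the study but have no rating, and it puts no second rate beside the first.

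Finally, counting missing as non-response is not neutral, as Step 3 shows. That argues against replacing the observed-case rate, not against showing a bound next to it.

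**Conclusion.** The point stands in conditional form. On the visible text, the primary response rate excludes treated subjects without a countable rating 8 weeks after last treatment, and is too high if non-responders are lost more often than responders.

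The bias is zero with equal loss and about +2 to +8 points under the assumed 5% against 30% to 50% dropout, for true rates of 80% to 90%. The gaps of about 5, 10 and 14 points at 5%, 10% and 15% missing assume an observed rate near 95%. They are worst-case bounds and should not be read as estimates of bias, because they treat every missing subject as a non-responder.

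All loss and response rates are assumptions. The 15% dropout and the hot deck imputation in the SAP belong to another trial and do not carry over. The redacted 10.4.1 may already settle the matter.

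**What to change.** Keep the observed-case rate. Unless 10.4.1 already provides it, add to Protocol 10.6 that:

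- the primary GAIS response rate is also reported with all treated subjects as denominator, counting a missing rating at 8 weeks after last treatment as non-response, and labelled as a conservative bound;
- the number of missing ratings is shown beside it by group and reason;
- it is stated whether a GAIS rating from an Early Termination visit counts toward the primary endpoint.

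The cost is a short addition to the text and one extra row in the primary table, with no new data collection. The downside is a second, less favourable figure that may understate the true rate, which the label makes clear. If few ratings are missing, the two figures will nearly agree and the main result is stronger for it.

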10.7 Interim analysis

Not applicable as this is an open study.

10.8 Withdrawals and deviations

All withdrawn subjects will be listed individually, including at least subject number, date and reason for withdrawal, and last visit performed.

Subjects with CSP deviations will be listed individually, including subject number and observed deviation. Depending on the seriousness of the deviation, subject might be excluded from the PP population, which shall be documented prior to database lock.

Deviations from the statistical plan will be documented in the statistical report.

10.9 Sample size

11. Protection of personal data

All processing of personal data must be carried out in accordance with national legislation concerning the protection of personal data, including the Personal Information Protection and Electronic Documents Act (PIPEDA). The Institution and the PI are responsible for complying with all requirements pursuant to national legislation in the country in which the Institution and the PI are located. The Sponsor will ensure that all requirements are complied with for data processing.

The informed consent form shall contain information about what personal data to be collected in the study and that this will be kept confidential. The provided information shall be sufficient to enable all subjects to give their consent not only to the participation in the study, but also to the processing of personal data. Such information includes information regarding the purposes of the collecting, processing, data transfer to other countries. If a subject decides to terminate the study prematurely, data collected before withdrawal of consent will be used in the evaluation of the study, however no new data may be collected. Authorized representatives from the Sponsor, clinical research organization (CRO) or a RA may visit the study site to perform audits/inspections, including SDV, i.e. comparing data in the subjects' medical records and the eCRF. Data and information shall be handled strictly confidential.

12. Quality Control and Quality Assurance

12.1 Quality control

On-site monitoring of the study will be arranged by the Sponsor according to GCP guidelines to verify that the rights and well-being of the subjects are protected, the reported data are accurate, complete, verifiable from source documents, and that the conduct of the study complies with the approved CSP, subsequent amendment(s), GCP and the applicable regulatory requirements.

Any CSP deviation shall be documented appropriately, verified, discussed, and collected by the monitor and appropriate actions will be taken. The PI is responsible for promptly reporting any deviations from the CSP that affects the rights, safety or well-being of the

subject or the scientific integrity of the study, including those that occur under emergency circumstances, to the Sponsor as well as the IEC if required by national regulations. Deviations will be reviewed to determine the need to amend the CSP or to terminate the study.

12.2 Quality assurance

The study site may be subject to quality assurance (QA) audit by the Sponsor as well as inspection by appropriate RA. It is important that the PI and other relevant study site personnel are available during the monitoring visits, possible audits, and inspections, and that sufficient time is devoted to the monitoring process.

Each participating member of the study site team shall provide a curriculum vitae (CV) or equivalent that demonstrates their qualifications to conduct the study.

It is the responsibility of the PI to ensure that all personnel involved in the study are fully informed of all relevant aspects of the study, including detailed knowledge of and training in all procedures to be followed. All Investigators and other responsible persons shall be listed together with their function in the study on the signature and delegation log.

12.3 Changes to the clinical study protocol

12.3.1 Amendments

The PI and other site personnel involved in the study must not implement any changes to the CSP without agreement with the Sponsor and prior review and documented approval from the IEC, except where necessary to eliminate an immediate hazard to the subjects. All changes to the final CSP must be documented in a dated and version-controlled written protocol amendment.

12.3.2 Deviations

The PI is not allowed to deviate from the CSP. However, under emergency circumstances, deviations from the CSP to protect the rights, safety and well-being of the subjects may proceed without prior approval of the Sponsor and the IEC. Such deviations should be documented and reported to the IEC as soon as possible. Any CSP deviation shall be reported in the deviation log, which will be verified, discussed, and collected, by the monitor and appropriate actions will be taken. Deviations will be reviewed to determine the need to amend the CSP or to terminate the study. Handling of CSP deviations will be performed as described in the monitoring manual. The PI is responsible for promptly reporting any deviations from the CSP that affects the rights, safety or well-being of the subject or the scientific integrity of the study, including those which occur under emergency circumstances, to the Sponsor (within 24 hours following detection) as well as the IEC if required.

13. Financing, Indemnification, and Insurance

The CTA outlines the compensation and payment terms of the study. The CTA must be signed before the first subject is screened in the study. If there are differences between the CTA and the CSP regarding certain rights and obligations, the CTA is the prevailing document. Q-Med AB's obligations in this clinical study are covered by Galderma's global general liability program. An insurance certificate will be provided upon request. The

Institution/PI is obligated to maintain insurance coverage for their obligations in the clinical study according to the CTA.

14. Publication Policy

The PI's, Institution's, and Q-Med AB's obligations regarding intellectual property rights, confidentiality, and publications are described in detail in the CTA.

